5.3 Agent Administration

5.3.1 *AZD1775*

Dose: 200mg po bid x 5 doses

AZD1775 will be administered bid for two and a half days starting concomitantly with the administration of cisplatin with cycle 2. The patient will take the first dose of AZD1775 in clinic on cycle 2 day 1, and subsequent doses that cycle can be taken at home. On cycle 2 day 1 and subsequent day 1 visits, AZD1775 and cisplatin may be administered concurrently. There is no preferential order of administration. The subsequent 4 additional doses of AZD1775 are to be taken in approximately 12 hour increments. Participants should take AZD1775on an empty stomach and should not have food 2 hours before or 2 hours after the dose. If the participant misses a dose by < 6 hours from scheduled dose, the dose should not be made up. If the participant vomits after the administration of AZD1775, the dose should not be readministered. AZD1775 should not be crushed, chewed or dissolved in water.

Premedication:

All patients must receive a 5-HT3 antagonist prior to each dose of AZD1775. In addition, dexamethasone 4 mg PO will be given with each AZD1775 dose as a minimum on the first day of dosing AZD1775 of every 3-5 days dosing period, unless contraindicated or not well-tolerated. Dexamethasone or the 5-HT3 antagonist may be given by IV.

5.3.2 *Cisplatin*

Administration

- **Dose**: Cisplatin 75mg/m² IVB q3 weeks (every 21 days, plus minus 3 days for scheduling issues). Cisplatin may be administered according to institutional guidelines at participating sites. The preferred guidelines are as described below.
- Infusion time: 60 minutes.
- **Pretreatment hydration**: Hydration may be achieved by IV infusion of 1 liter of sodium chloride 0.9% (±potassium 20 meq) over 1-2 hours prior to Cisplatin infusion.
- **Pretreatment Magnesium Supplementation**: As needed, give prior to Cisplatin, Magnesium Sulfate 2 GM IV×1.
- Treatment: Ensure there is adequate urine output averaging at least 100cc/hr prior to Cisplatin infusion. As needed, give 12.5mg IVB of MANNITOL 25% 30 minutes prior to Cisplatin infusion. Mix Cisplatin in 100-500ml sodium chloride 0.9% and infuse IVB over 60 minutes. Post-treatment hydration: Participants should receive 1 liter of sodium chloride 0.9% (±potassium 20 meq) IV over 1-2 hours after Cisplatin administration.
- **Post-treatment hydration:** Participants should receive 1 liter of sodium chloride 0.9% (±potassium 20 meg) IV over 1-2 hours after Cisplatin administration.

Caregiver Precautions:

- Qualified personnel who are familiar with procedures that minimize undue exposure to themselves and to environment should undertake the preparation, handling, and safe disposal of chemotherapeutic in a self-contained, protective environment.
- Discard unused portions of infectable chemotherapeutic agents that do not contain a bacteriostatic agent or that are prepared with unpreserved diluents (i.e., sterile water for injection, USP, or 0.9% sodium chloride for injection, USP) within 8 hours of vital entry to minimize the risk of bacterial contamination.
- The total administered dose of chemotherapy may be rounded up or down within a range of 5% of the actual calculated dose.

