- 3.1.11 Availability of a tissue block from initial breast cancer diagnosis and/or metastatic recurrence. If a tissue block is not available, 10-20 unstained slides may be provided as an alternative. If unstained slides will be provided, they should not be sent until specifically requested by the DFCI study coordinator. If archival tumor tissue is not available, a fresh biopsy may be performed.
- 3.1.12 All patients with biopsy-accessible disease must be willing to undergo paired research biopsies. These biopsies will occur 5-48 hours after the C1D1 cisplatin dose (ie. C1D2or C1D3) and 5-8hrs (+/- 24hrs) after the last dose of AZD1775 on C2D3. The exact timing of the biopsy relative to receipt of study treatment should be accurately recorded.
 - Biopsies may be done with local anesthesia or intravenous conscious sedation, according to standard institutional guidelines.
 - Research biopsies requiring general anesthesia are not allowed on this protocol unless a biopsy is being obtained simultaneously for clinical reasons, in the judgment of the patients' treating physician.
 - Patients who undergo an attempted on-treatment research biopsy and in whom inadequate tissue is obtained are still eligible to continue protocol therapy. They will not be required to undergo a repeat biopsy attempt.
 - If dosing is delayed placing the biopsy outside of the allowable window, the biopsy should be rescheduled to be within the window. If not feasible, the biopsy should be obtained as close to within the window as possible.
 - Fine needle aspirates (FNA) is not allowed
- 3.1.13 Female subjects of childbearing potential must have a negative serum pregnancy test at screening.
- 3.1.14 The effects of AZD1775 on the developing human fetus are unknown. Women of child-bearing potential and men must agree to use enhanced methods of contraception. All women are considered to be of childbearing potential unless they fulfill one of the following criteria at screening:
 - Post-menopausal defined as age ≥50 and amenorrheic for at least 12 months OR
 - Women age <50 if they have been amenorrheic for at least 12 months and have a serum follicle-stimulating hormone (FSH) and luteinizing hormone (LH) level in the postmenopausal range (per institutional standards).
 - If women have documentation of irreversible surgical sterilisation by hysterectomy, bilateral oophorectomy, or bilateral salpingectomy, or bilateral tubal ligation, they are considered post-menopausal.

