5. TREATMENT PLAN

5.1 Treatment Regimen

Treatment will consist of one cycle (21 days) of cisplatin monotherapy (cisplatin 75 mg/m2 IV) followed by combination therapy of AZD1775 plus cisplatin starting 21 days later. AZD1775 will be administered as twice daily oral dosing (AZD1775 200mg po bid) x 5 doses for 2.5 days, in combination with cisplatin 75 mg/m2 IV every 21 days. Cycle length is 21 days long. Treatment will be administered on an outpatient basis. Reported adverse events and potential risks are described in Section 7. Appropriate dose modifications are described in Section 6. No investigational or commercial agents or therapies other than those described below may be administered with the intent to treat the participant's malignancy.

	Regimen Description				
Agent	Premedications; Precautions	Dose	Route***	Schedule	Cycle Length
AZD1775*	See Section 5.4	200 mg	PO	Twice daily x 5 doses From Cycle 2	21 days (3 weeks)
Cisplatin	See Section 5.3.2	75 mg/m2	IV 60 minutes	Days 1 From Cycle 1	

* The participant will be requested to maintain a medication diary of each dose of medication. The medication diary will be returned to clinic staff at the end of each cycle.

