6.1 Dose Delays and Modifications for AZD1775

Participants can have a maximum of 2 dose modifications (if applicable) throughout the course of the study for toxicities. Participants who require more than 2 dose modifications may remain on study and continue with cisplatin monotherapy per investigator discretion. In the event that a participant is not willing to dose reduce AZD1775, they may continue with cisplatin monotherapy per investigator discretion.

In the event of toxicity, it is recommended that the investigator first modify the dose of AZD1775; however the investigator may choose to first modify the chemotherapy dose instead, in consultation with the Principal Investigator. If a second dose reduction is necessary during combination therapy, the dose of chemotherapy or AZD1775 may be modified. This decision should be made jointly by the treating physician and the Principal Investigator. Participants who experience toxicity that the investigator finds attributable to AZD1775 will have their AZD1775 dose reduced by 1 dose level as shown in Table 6-1. A participant's dose may be re-escalated at the discretion of the principal investigator.

If Day 1 dosing is delayed, all assessments will be delayed to accordingly.

Table 6-1 DOSE MODIFICATION OF AZD1775

Dose Level	AZD1775 Dose
0	200mg, twice daily x 5 doses
-1	175mg, twice daily x 5 doses
-2	150mg, twice daily x 5 doses
-3	125mg, twice daily x 5 doses

Nausea	Management/Next Dose for AZD1775
≤ Grade 1	No change in dose
Grade 2	Hold until ≤ Grade 1. Resume at same dose level.
Grade 3	Hold* until < Grade 2. Resume at one dose level lower, if indicated.**
Grade 4	Discontinue treatment and follow for disease progression
4	

^{*}Participants requiring a delay of >3 weeks should discontinue AZD1775.

All patients must receive a 5-HT3 antagonist prior to each dose of AZD1775. Additional doses of 5-HT3 antagonist may be used if needed. In addition, dexamethasone 4 mg PO will be given with each AZD1775 dose as a minimum on the first day of dosing AZD1775 of every 3-5 days dosing period, unless contraindicated or not well-tolerated. Dexamethasone may be continued on further days of dosing, potentially at a lower dose. Dexamethasone or the 5-HT3 antagonist may be given by IV.

Promethazine (Phenergan), prochlorperazine (Compazine), and benzodiazepine may still be used as additional adjunctive treatments during AZD1775 therapy.

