9.2.3.2 Collection of Specimen(s)

Biopsies will be collected at C1D1 5-48hrs after Cisplatin administration and at C2D3 within 5-8hrs (+/- 24hrs) after the last dose of AZD1775 administration. If dosing is delayed placing the biopsy outside of the allowable window, the biopsy should be rescheduled to be within the window. If not feasible, the biopsy should be obtained as close to within the window as possible.

Tissue specimens will be collected from recurrent or metastatic lesions using standard institutional procedures. The amount of tissue collected will follow the guidelines listed below. If a participant has more than one site of disease, only one site needs to be biopsied in order to go on to the study and the site is left to the discretion of the patient and their treating physician. Fine need aspirates (FNA) is not allowed. Participants who undergo a research biopsy procedure for the purpose of this protocol, and in whom inadequatetissue is obtained, are still eligible and are not required to undergo a repeat biopsy in order to enter the study.

Breast: A goal of 3-6 core biopsy specimens will be obtained using standard institutional guidelines for a diagnostic core biopsy of a breast mass.

Skin/chest wall: A goal of 1-2 5-mm punch biopsies will be obtained.

Lymph node: A goal of 3-6 core biopsy specimens will be obtained using an 18-gauge needle.

Liver: A goal of 3-6 core biopsy specimens will be obtained using an 18-gauge needle.

Lung: Because of the risk of pneumothorax associated with core needle biopsies of lung nodules, no core biopsies of lung nodules will be performed on this protocol, unless they are clinically indicated.

Bone: Because the yield of malignant tissue from bone biopsies tends to be relatively low, if a participant has another accessible site of disease (i.e. skin, lymph node, liver), that site should be biopsied preferentially. If bone is the only biopsy-accessible site, then a goal of 3-6 core biopsy specimens will be obtained using an 11-13gauge needle.

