10. STUDY CALENDAR

Baseline evaluations are to be conducted within 1 week prior to start of protocol therapy unless otherwise specified. Informed consent, scans and x-rays must be done \leq 4 weeks prior to the start of therapy. In the event that the participant's condition is deteriorating, laboratory evaluations should be repeated within 48 hours prior to initiation of the next cycle of therapy.

Assessments must be performed prior to administration of any study agent. Study assessments and agents should be administered within \pm 3 days of the protocol-specified date, unless otherwise noted. End of treatment assessments may be performed within 30 days of treatment discontinuation.

	Baseline	Cycle 1 Day 1	Cycle 2 Day 1	Cycle 2 Day 21	Cycle 3 Day 1	Cycle 4+ Day 1	Cycle 4+ Day 21	End of Treatment	Follow-Up ¹
AZD1775 ^a			X		X	X			
Cisplatin ^b		X	X		X	X			
Informed consent	X ^m								
Demographics	X								
Medical history	X								
Physical exam	X	X	X		X	X		X	
Vital signs ^c	X	X	X		X	X		X	
Weight ^d	X	X	X		X	X		X	
Height	X								
Performance status	X	X	X		X	X		X	
Adverse Event Assessment		X	X		X	X		X	
CBC w/diff, plts	X	X	X		X	X		X	
Serum chemistry ^e	X	X	X		X	X		X	
B-HCG ^f	X								
EKG ^g	X							X	
Radiologic evaluationh	X			X			X		X
Archival tumor tissue	X								
Research biopsyi		X	X						
cfDNA Blood collection ^j	X				\mathbf{X}^{j}	\mathbf{X}^{j}		X ^j	
Blood for genomic sequencing ^k		X						vole. Day 1 docing is	

- a. AZD1775: 200mg (PO) BID beginning with Cycle 2 Day 1. The patient will take 5 doses of AZD1775 each cycle. Day 1 dosing is to be done in the clinic; subsequent doses can be taken at home. The 4 additional doses of AZD1775 are to be taken in approximately 12 hour increments. Patients should take AZD1775 either two hours before or two hours after a meal.
- b. Cisplatin: 75mg/m² (IV) given on Day 1 of each 21-day cycle (+/- 3 days)
- c. Vital signs should be collected pre-dose on dosing days and are to include measurements of heart rate, respiratory rate, systolic and diastolic blood pressure while the patient is in a seated position, and oral or tympanic temperature.
- d. Weight adjustments for cisplatin will be done according to institutional standards.
- e. Albumin, alkaline phosphatase, total bilirubin, bicarbonate, BUN, calcium, chloride, creatinine, glucose, LDH, phosphorus, potassium, total protein, SGOT [AST], SGPT [ALT], sodium, magnesium

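### The missed-dose rule for AZD1775 in section 5.3.1 appears reversed: it drops a dose less than 6 hours late and is silent on later ones

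*Combined protocol and SAP*

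**What the plan says.** Section 5.3.1 sets the AZD1775 regimen: "Dose: 200mg po bid x 5 doses". The first dose of cycle 2 is taken in clinic and the rest of that cycle's doses may be taken at home. On spacing it says: "The subsequent 4 additional doses of AZD1775 are to be taken in approximately 12 hour increments".

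The missed-dose rule follows in the same paragraph: "If the participant misses a dose by < 6 hours from scheduled dose, the dose should not be made up". The next sentence deals with vomited doses, which are not given again. Nothing is said about a dose 6 or more hours late.

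Other places that touch on dosing:

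- Section 10, Study Calendar, footnote a repeats the spacing ("The 4 additional doses of AZD1775 are to be taken in approximately 12 hour increments") and has no missed-dose rule.
- Section 5.1 asks for a diary ("The participant will be requested to maintain a medication diary of each dose of medication"), but the diary text is not in the documents.
- Section 6.1 covers holds and reductions for toxicity only.
- Section 9.2.3.2 times the cycle 2 research biopsy from the last dose: "at C2D3 within 5-8hrs (+/- 24hrs) after the last dose of AZD1775 administration".

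**The concern.** On a schedule with doses about 12 hours apart, a missed-dose rule normally lets a patient take a dose that is only a little late and tells the patient to skip one that is close to the next. The sentence in section 5.3.1 does the opposite. The doses nearest their planned time are the ones it says not to make up, and those furthest from it have no rule.

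AZD1775 is the drug under test, and late home doses are foreseeable. Section 5.3.1 requires an empty stomach for 2 hours on either side of each dose and an antiemetic before each one, so a patient who has just eaten has to wait. A site that follows the sentence withholds study drug from that patient. A site that sensibly has the patient take the dose late departs from the protocol. The same event could be handled differently from site to site, and the text gives no ground for calling either handling wrong in practice.

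**Working it through.** No sample-size or error-rate figure is involved, and the plan states no figure on this point to reproduce. The check is a reading of the rule against the schedule, with simple arithmetic.

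**Inputs**

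- Dose: 200 mg, 5 doses per cycle (section 5.3.1).
- Spacing: about 12 hours (section 5.3.1; section 10, footnote a).
- Threshold: 6 hours, with a less-than sign (section 5.3.1).
- Cycle 2 biopsy: 5 to 8 hours after the last dose, with a 24-hour allowance either way (section 9.2.3.2).

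**1. What the rule covers, by lateness L of a dose**

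| Lateness | As written | Inequality reversed | Counted back from the next dose |
|---|---|---|---|
| 0 < L < 6 h | do not make up | may be taken | may be taken |
| L = 6 h | no instruction | may be taken | may be taken |
| 6 h < L < 12 h | no instruction | do not make up | do not make up |

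The last column follows from the spacing: less than 6 h before the next dose means L > 12 − 6 = 6 h. The two plausible repairs therefore agree wherever another dose follows. They part only at the fifth dose, which has no next dose to count back from. A replacement stated in terms of lateness covers all the doses.

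**2. Size of one literal application**

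- Full cycle: 5 × 200 = 1000 mg.
- One dose dropped: 4 × 200 = 800 mg.
- Loss: 200 / 1000 = 20% of that cycle's AZD1775.

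With nominal dose times of 0, 12, 24, 36 and 48 h, dropping dose 2, 3 or 4 leaves a gap of 24 h (24 − 0, 36 − 12 or 48 − 24).

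**3. Does any other text correct it?**

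Sections 5.1, 5.4, 5.5 and 6.1 and the calendar footnotes contain no other rule for late or missed doses. The vomiting sentence in 5.3.1 concerns doses already taken.

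**4. What the replacement rule does**

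- Shortest gap between doses: 12 − 6 = 6 h.
- Latest permitted fifth dose: 48 + 6 = 54 h.
- Biopsy planned from an on-time fifth dose: 48 + 5 = 53 h to 48 + 8 = 56 h.
- Biopsy timed from a fifth dose at 54 h: 54 + 5 = 59 h to 54 + 8 = 62 h.
- If left at its planned time, that biopsy would fall between 1 h before (53 − 54) and 2 h after (56 − 54) the last dose. It would therefore need to move to keep the 5-to-8-hour target.

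**The case against.** The strongest reply is that this is a drafting slip whose intent is easy to recover. The spacing is only approximate, so a dose 2 hours late can reasonably count as on schedule. Both repairs lead to nearly the same rule, and sites would probably apply it. The sign may also have been altered when the PDF was read.

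Part of this stands: it is a wording error, and the likely intent is clear for doses 2 to 4. But the approximate spacing has no stated tolerance and cannot excuse a delay of 4 or 5 hours, which the rule itself says to skip. A misread sign is possible in principle, but nothing in the documents shows it.

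A reader might also infer more than the documents support:

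- **That a dropped dose is worse than a formal dose reduction.** Dose level −1 ("175mg, twice daily x 5 doses") gives 5 × 175 = 875 mg, more than 800 mg. But that sets a loss in one cycle against a reduction that normally carries into later cycles. Table 6-1 also allows level −2, at 5 × 150 = 750 mg, and the plan already accepts the loss of vomited doses.
- **That the paired-biopsy result is compromised.** If dose 5 is dropped, the last dose is at 36 h, and a biopsy kept at 53 to 56 h falls 17 to 20 h after it (53 − 36; 56 − 36). That is inside the outer limit of 8 + 24 = 32 h. Section 3.1.12 also requires that "The exact timing of the biopsy relative to receipt of study treatment should be accurately recorded", so the shift would be visible. The same shift arises under any rule that can skip dose 5, including the one proposed here. Section 9.2.3.2 already times the biopsy from the last AZD1775 dose, and section 9.1 labels the biomarker analyses exploratory.

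**Conclusion.** The concern holds as a wording error in an operative dosing instruction. Followed literally, section 5.3.1 drops a mildly late AZD1775 dose, at a cost of 20% of that cycle's drug per event, and gives no instruction at 6 hours or more. Nothing elsewhere in the documents corrects it.

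The 20% assumes full dose (200 mg × 5) and one dropped dose in the cycle. It is a loss per event, not an expected loss in exposure: the frequency of late doses is not in the documents, and the diary may have told patients something more sensible. A reader might infer diluted efficacy or lost power; the documents give no basis for that. The two-stage design in section 13.1 and the analysis population in section 13.2 are untouched. The point is worth correcting because it governs how the investigational drug is taken and costs almost nothing to put right.

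**What to change.** Replace the sentence in section 5.3.1 with: *If a dose is 6 hours or less late, take it and take any remaining doses at their scheduled times; if it is more than 6 hours late, skip it and do not make it up.* This wording also covers the fifth dose, so no separate rule is needed for it.

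The sponsor should confirm the 6-hour cutoff, since the documents give no pharmacokinetic support for a 6-hour minimum gap. The patient diary should carry the same wording.

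The cost is one sentence and matching diary text, with no added visits, procedures or patients. The small downside is that a late fifth dose in cycle 2 may require the research biopsy to be moved by up to 6 hours to keep its target interval. The existing allowance and the rescheduling text in section 9.2.3.2 leave room for that.

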5.4 General Concomitant Medication and Supportive Care Guidelines

The major pathway for metabolism of AZD1775 involves CYP3A4. Therefore AZD1775 may be prone to drug-drug interactions when co-administered with drugs that are known to be moderate or potent inhibitors/inducers or substrates of CYP3A4.

Prohibited Medication

Patients may receive other medications that the investigator deems to be medically necessary, with the specific exception of non-protocol specified chemotherapy, radiotherapy, anti-neoplastic biological therapy or other investigational agents. Patients who require the use of any of the aforementioned treatments for clinical management should be removed from the study.

Drugs known to be moderate or potent inhibitors/inducers of CYP3A4 or substrates of CYP3A4 with narrow therapeutic windows are generally prohibited. However, some agents (e.g. midazolam, fentanyl, or any other agent used for anesthesia purposes) with which participants will have short term exposure are permissible. List of agents known to be moderate or strong inhibitors/inducers of CYP3A4 or substrates of CYP3A4 with narrow therapeutic widows includes:

- Inhibitors of CYP3A4: azole antifungals (ketoconazole, iraconazole, fluconazole and voriconazole), macrolide antibiotics (erythromycin, clarithromysin), cimetidine, aprepitant, HIV protease inhibitors, and nefazodone
- Inducers if CYP3A4: phenytoin, barbiturates and rifampicin
- Substrates of CYP3A4: statins (lovastain, simvastain [Atorvastatin is also prohibited because of BCRP effect]), midazolam, terfenadine, astemizole, and cisapride

Please refer to Table 5.5-1 for other concomitant medications including a list of inhibitors, inducers and substrates of CYP3A4. This list is not all inclusive, and, the Principal Investigator will determine if they are known to significantly influence CYP3A4. Supportive care with a CYP3A4 inhibitor / inducer / substrate according to institutional guidelines in the context of standard of care chemotherapy will be exempt in some cases provided it is administered within the guidance of the protocol (Please refer to Supportive Care below). Concomitant treatment with aprepitant is not allowable per protocol.

Table 5.5-1
DRUG INTERACTIONS
TABLE OF CYP3A INHIBITORS, INDUCERS, AND SUBSTRATES

EXAMPLES OF CYTOCHROME P450 ISOENZYME INHIBITORS AND INDUCERS			
Inhibitors		Inducers	
amiodarone	indinavir	barbiturates	phenobarbital
aprepitant	itraconazole	carbamazepine	phenytoin
cimetidine	ketoconazole	efavirenz	rifampin
ciprofloxacin	mibefradil	glucocorticoids	St. John's Wort
clarithromycin	mifepristone	modafinil	troglitazone
delabiridine	nefazodone	nevirapine	_
dilitiazem	nelfinavir		
erythromycin	norfloxacin		
fluconazole	ritonavir		
fluvoxamine	saquinavir		
gestodene	troleandmycin		
grapefruit juice			

http://medicine.iupui.edu/flockhart/

Classification of Substrates

Examples of sensitive CYP3A substrates or CYP3A substrates with narrow therapeutic range			
Sensitive CYP3A substrates ¹		CYP3A Substrates with Narrow therapeutic range ²	
budesonide	midazolam	alfentanil	pimozide
buspirone	saquinavir	astemizole(a)	quinidine
eplerenone	sildenafil	cisapride(a)	sirolimus
eletriptan	simvastatin	cyclospotine	tacrolimus
felodipine	triazolam	diergotamine	terfenadine(a)
fluticasone	vardenafil	ergotamine	, ,
lovastatin		fentanyl	

Note that this is not an exhaustive list.

- 1. Sensitive CYP3A4 substrates refers to drugs whose plasma AUC values have been shown to increase 5-fold or higher when co-administered with a known CYP2A inhibitor.
- 2. CYP3A substrates with narrow therapeutic range refers to drugs whose exposure-response indicates that increases in their exposure levels by the concomitant use of CYP3A inhibitors may lead to serious safety concerns (e.g., Torsades de Pointes).
- (a) Not available in the United States.

In light of *in vitro* data which suggests that AZD1775 may be a CYP2C8, CYP2C9, and CYP2C19 inhibitor, caution should be exercised with concomitant administration of AZD1775 and agents that are sensitive substrates of CYP2C8, CYP2C9, CYP2C19, or substrates of these enzymes with narrow therapeutic range. Please refer to Table 5.5-2 for a list of sensitive substrates of CYP2C8, CYP2C9, and CYP2C19, or substrates of these enzymes with narrow therapeutic range. This list is not all inclusive, and for other concomitant medications, the Principal Investigator will determine if they are known to significantly influence CYP2C8, CYP2C9, and/or CYP2C19.

Table 5.5-2 DRUG INTERACTIONS TABLE OF CYP2C8, CYP2C9, AND CYP2C19 SENSITIVE SUBSTRATES

Sensitive substrates of CYP2C8, CYP2C9, and CYP2C19 and substrates with a narrow therapeutic range for these enzymes

Repaglinide, paclitaxel, warfarin, phenytoin, omeprazole, s-mephenytoin

Note that this is not an exhaustive list.

In light of *in vitro* data which suggests that AZD1775 may be a substrate for human P-glycoprotein (P-gp) caution should be exercised when agents that are inhibitors or substrates of P-gp are administered concomitantly with AZD1775. Please refer to Table 5.5-3 for a list of inhibitors or substrates of P-gp. This list is not all inclusive, and for other concomitant medications, the Principal Investigator will determine if they are known to significantly

influence P-gp.

Table 5.5-3 DRUG INTERACTIONS TABLE OF INHIBITORS OR SUBSTRATES OF P-GP

Inhibitor of P-gp	Substrates of P-gp
ritonavir, cyclosporine, verapamil,	digoxin, fexodenadine, indinavir, vinctistine,
erythromycin, ketoconazole, itraconazole,	colchicines, topotecan, paclitaxel
quinidine	

Note that this is not an exhaustive list.

Supportive Care

Patients should receive optimal supportive care throughout the study, including transfusions of blood and blood products, antibiotics, antiemetics, when appropriate. The reason(s) for treatment, dosage, and dates of treatment should be recorded.

• Nausea/vomiting:

All patients must receive a 5-HT3 antagonist prior to each dose of AZD1775. Additional doses of 5-HT3 antagonist may be used if needed. In addition, dexamethasone 4 mg PO will be given with each AZD1775 dose as a minimum on the first day of dosing AZD1775 of every 3-5 days dosing period, unless contraindicated or not well-tolerated.

Dexamethasone may be continued on further days of dosing, potentially at a lower dose. Dexamethasone or the 5-HT3 antagonist may be given by IV.

Promethazine (Phenergan), prochlorperazine (Compazine), and benzodiazepine may still be used as additional adjunctive treatments during AZD1775 therapy.

Please note: aprepitant [Emend] and fosaprepitant are not permitted due to known DDIs.

Patients should be strongly encouraged to maintain liberal oral fluid intake.

Suitable alternative medications may be used, with adequate justification, where the use of any of the above medications might interfere with other study procedures or are deemed insufficient.

• Diarrhea: Diarrhea should be treated promptly with appropriate supportive care, including administration of an anti-diarrheal agent according to standard practice guidelines. Anti-diarrheal agents should not be taken prophylactically. Patients should be instructed to begin taking anti-diarrheal medication at the first sign of: 1) poorly formed or loose stool, 2) occurrence of more bowel movements than usual in one day or 3) unusually high volume of stool. Anti-diarrheal agents should be deferred if blood or mucus is present in the stool or if diarrhea is accompanied by fever. In this setting, appropriate diagnostic microbiologic specimens should be obtained to exclude an infectious etiology. Patients should also be advised to drink liberal quantities of clear fluids to help prevent dehydration. Octreotide can also be considered to aid with management of diarrhea. If diarrhea is severe (ie. requiring IV hydration) and/or associated with fever or grade 3 or 4 neutropenia, broad spectrum

antibiotics should be considered. Additionally, hospitalization for IV hydration and eletrolyte correction should be considered.

Patients should be instructed to notify the Investigator or research staff for the occurrence of blood or black stools, symptoms of dehydration, fever, inability to take liquids by mouth, and inability to control diarrhea within 24 hours of using loperamide or other prescribed antidiarrheal medications.

- **Anemia**: Transfusions and/or erythropoietin may be utilized as clinically indicated for the treatment of anemia, but should be clearly noted as concurrent medications.
- **Neutropenia**: Colony-stimulating factors including G-CSF, pegylated G-CSF or GM-CSF according to Institutional Standards.
- **Febrile Neutropenia:** Patients experiencing febrile neutropenia with significant symptoms should be managed in a hospital setting according to standard procedures, with the urgent initiation of IV antibiotic therapy. Patients with febrile neutropenia without symptoms should be managed according to standard guidelines.
- Thrombocytopenia: Transfusion of platelets may be used if clinically indicated.
- Patients requiring radiation or surgery for palliation of a non-target lesion that have not measurably increased in size according to RECIST will be considered to have progressed.
- Participants may receive intravenous fluids on study.
- Bisphosphonates are allowed while on study.

